- Serum blood urea nitrogen, creatinine, estimated glomerular filtration rate, INR, sodium, potassium, bicarbonate, ALT, AST, alkaline phosphatase, total bilirubin, albumin, hemoglobin, serum or urine hCG for females of childbearing potential, HCV quantitative RNA, hepatitis B surface antigen and hepatitis B core antibody total;
- For liver transplant, presence or absence of hepatocellular carcinoma;
- For liver transplant, presence and severity of hepatic encephalopathy and ascites;
- For liver transplant, Lab MELD-Na, MELD exception score (if any) and Child-Pugh score (Appendix 4) at the time of transplant;
- For kidney transplant, panel reactive antibody.

Donor data Pre-Transplant Day:

- Age, sex, cause of death (brain or cardiac);
- UNOS region;
- For kidney transplant, kidney donor profile index;
- HCV RNA NAT testing, HCV genotype, hepatitis B core antibody;
- Sample for possible baseline resistance associated substitutions;
- Sample for serum banking;
- Liver biopsy: stage of fibrosis and estimated percentage of fat.

Transplant surgery data:

- For liver transplant, surgical technique: piggyback vs other;
- Cold and warm ischemia times (in hours);
- Time and date of transplant (time of reperfusion for liver transplant).

Recipient data in the post-transplant period:

- Time and date of first administration of study drug;
- Interval (in days) between time of transplant and time and date of first administration of study drug;
- HCV RNA on day 3 after transplant, If result is “HCV RNA not detected”, HCV RNA to be repeated on day 7 after transplant and then weekly until HCV RNA is detected;
- Serum blood urea nitrogen, creatinine, estimated glomerular filtration rate, INR, sodium, potassium, bicarbonate, ALT, AST, alkaline phosphatase, total bilirubin, albumin, hemoglobin, and immunosuppressant level and dosage on treatment days 1, 3, and 7; weekly throughout the treatment period; at the end of treatment; and 4, 12, and 24 weeks after discontinuation of therapy;
- serum or urine serum hCG for females of childbearing potential at weeks 4 and 8 and at end of treatment;
- Serial quantitative HCV RNA testing will be done on Day 1, treatment weeks 1 and 4; end of treatment; and weeks 4, 12 and 24 after discontinuation of therapy;
- Testing for resistance associated substitutions if virologic failure;
- Length of index hospital stay (in days);
- Number, length and reason for subsequent post-transplant admissions (if any);

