- Concomitant medications of interest;
- Interruptions of antiviral therapy > 72 hours.

Resistance Monitoring

Plasma samples will be collected for viral sequence analysis and possible phenotypic testing from the donor at baseline and from the recipient at treatment failure (if it occurs).

Subject identification number assignment

Subject Identification (ID) numbers will be assigned sequentially at each site to each subject who has signed informed consent (Part 1). A new subject ID number (indicated by the prefix “ST-” followed by the ID number previously assigned at the time of signing informed consent Part 1) will be assigned when eligibility has been confirmed, the subject has signed informed consent Part 2 and the subject undergoes transplant surgery. If a patient discontinues from the study, the Subject ID Number will not be reused.

Study Visits

1st visit: Screening Visit

This visit is anticipated to require 1 hour of the subject's time. During this visit, the following will take place:

- Review of eligibility criteria;
- Informed consent;
- Assignment of subject ID number.

2nd visit: Pre-Transplant Day

Screening/baseline visit is anticipated to require 1 hour of the subject's time. During this visit, the following will take place:

- Confirmation of consent signed and documentation of subject's willingness to proceed with HCV positive donor;
- Review of eligibility criteria;
- Laboratory tests including Quantitative HCV RNA, hepatitis B surface antigen, Serum blood urea nitrogen, creatinine, estimated glomerular filtration rate, INR, sodium, potassium, bicarbonate, ALT, AST, alkaline phosphatase, total bilirubin, albumin, hemoglobin, serum or urine hCG for females of childbearing potential;
- Assessment of presence and severity of ascites and hepatic encephalopathy;
- Assignment of subject ST-ID number.

3rd visit: Day 3 after transplant

- Quantitative HCV RNA. (if "HCV RNA not detected", repeat day 7 after transplant. If result is "HCV RNA not detected", HCV RNA to be repeated weekly after transplant until detected)

Day 1 (The day study drug commences)

- Confirm recipient still meets eligibility criteria;
- First administration of study drug;
- Laboratory tests including serum blood urea nitrogen, creatinine, estimated glomerular filtration rate, INR, sodium, potassium, bicarbonate, ALT, AST, alkaline phosphatase, total bilirubin, albumin, hemoglobin, immunosuppressant level, and quantitative HCV RNA.;

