- Laboratory tests including serum blood urea nitrogen, creatinine, estimated glomerular filtration rate, sodium, potassium, bicarbonate, ALT, AST, alkaline phosphatase, total bilirubin, albumin, hemoglobin, INR, and immunosuppressant level;
- Serum or urine hCG for females of childbearing potential at Follow Up Week 4;
- Hepatitis B surface antigen at Follow Up Week 4;
- Quantitative HCV RNA;
- Concomitant medications of interest including immunosuppressant on follow up week 4;
- Immunosuppressant dose;
- Assessment for AEs on Follow Up Week 4.

Early End of Treatment or Treatment Failure visit

This unscheduled visit will occur if the subject discontinues study drug prior to planned end of treatment for any reason OR the subject has been determined to have viral breakthrough or relapse. This visit must occur within 2 weeks of stopping treatment or recognition of viral breakthrough or relapse. Each visit is anticipated to require 30 minutes of the subject's time. The following events will take place:

- Clinical examination;
- Laboratory tests including serum blood urea nitrogen, creatinine, estimated glomerular filtration rate, INR, sodium, potassium, bicarbonate, ALT, AST, alkaline phosphatase, total bilirubin, albumin, hemoglobin, and immunosuppressant level;
- Quantitative HCV RNA and HCV genotype;
- Testing for HCV resistance associated substitutions;
- Concomitant medications of interest including immunosuppressant;
- Assessment for AEs.

Visit Windows

The study visit windows are +/- 2 days for the day 3 visit, +/- 4 days for the weekly on treatment visits and end of treatment visit, and +/- 10 days for the follow up visits

End of Study Definition

End of study is considered to be completion of the Follow Up Week 24 Visit. Subjects who enter the Virologic Failure Substudy will also follow an additional

Schedule of Assessments for the Virologic Failure Substudy (See Appendix 3a).

Sample Storage

Residual biological samples will be frozen and stored at the individual study sites. No

human genetic testing will be performed without express consent of the study subjects. At the conclusion of this study, these samples may be retained in storage per individual institution policy.

Study Visits for Virologic Failure Substudy

Study visits for the Virologic Failure Substudy may coincide with visits for the main study. When this occurs, laboratory assessments for the main study may also be used for the Virologic Failure Substudy.

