Day 1 (The day SOF/VEL/VOX commences)

- First administration of study drug;
- Laboratory tests including serum blood urea nitrogen, creatinine, estimated glomerular filtration rate, INR, sodium, potassium, bicarbonate, ALT, AST, alkaline phosphatase, total bilirubin, albumin, hemoglobin, immunosuppressant level, and quantitative HCV RNA.
- Concomitant medications of interest including immunosuppressant;

On HCV treatment visits

These 3 visits will occur in the outpatient clinic per the schedule of assessments on Week 1, Week 4, and Week 8. It is anticipated that each of these visits will require 30 minutes of the subject's time. The following events will take place:

- Clinical examination;
- Laboratory tests including serum blood urea nitrogen, creatinine, estimated glomerular filtration rate, sodium, potassium, bicarbonate, ALT, AST, alkaline phosphatase, total bilirubin, albumin, hemoglobin, INR, and immunosuppressant level;
- Serum or urine hCG for females of childbearing potential at weeks 4 and 8;
- Quantitative HCV RNA on weeks 1 and 4;
- Hepatitis B surface antigen on week 4;
- Concomitant medications of interest including immunosuppressant;
- Assessment for AEs.

End of HCV treatment visit

This visit will occur at the end of antiviral treatment at the outpatient clinic. It is anticipated to require 30 minutes of the subject's time. The following events will take place:

- Clinical examination;
- Laboratory tests including serum blood urea nitrogen, creatinine, estimated glomerular filtration rate, INR, sodium, potassium, bicarbonate, ALT, AST, alkaline phosphatase, total bilirubin, albumin, hemoglobin, and immunosuppressant level;
- Serum or urine hCG for females of childbearing potential;

- Quantitative HCV RNA;
- Concomitant medications of interest including immunosuppressant;
- Assessment for AEs.

Post-HCV treatment Follow Up visits

These three visits will occur at 4, 12, and 24 weeks after discontinuation of antiviral treatment. Follow Up visits 4 and 12 will take place in the outpatient clinic while Follow Up Week 24 will occur either in the transplant clinic or local laboratory and may also include a telephone call to confirm the dose of the immunosuppressant medications. Each visit is anticipated to require 15-30 minutes of the subject's time. The following events will take place:

- Clinical examination (Follow Up visits 4 and 12 only;)

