*HCV RNA will be checked day 3 after transplant. If HCV RNA is positive, may proceed with Day 1. If, If result is “HCV RNA not detected”, HCV RNA to be repeated on day 7 after transplant and then weekly until HCV RNA is detected. HCV RNA must be positive before starting study drug.

^a Age, sex, ethnicity, race, weight, BMI, type of transplant (liver or kidney), indication for transplant, BUN, creatinine, GFR, INR, sodium, potassium, bicarbonate, ALT, AST, alkaline phosphatase, total bilirubin, albumin, hemoglobin, presence of HCC (liver), CP score (liver), lab MELD (liver), exception MELD (liver), panel reactive antibody (kidney), quantitative HCV RNA, HBV surface antigen, HBV core antibody

^b Age, sex, cause of death, UNOS region, kidney donor profile index (kidney), HCV nucleic acid test, HCV genotype, HBV core antibody, sample for baseline resistance associated substitution (RAS), sample for serum banking, liver biopsy fibrosis stage and fat percentage

^c BUN, creatinine, GFR, INR, sodium, potassium, bicarbonate, ALT, AST, alkaline phosphatase, total bilirubin, albumin, hemoglobin, and immunosuppressant level and dosage.

^d hepatitis B surface antigen added to other evaluations

^e BUN, creatinine, GFR, INR, sodium, potassium, bicarbonate, ALT, AST, alkaline phosphatase, total bilirubin, albumin, hemoglobin, HCV genotype, sample for RAS, and immunosuppressant level and dosage.

^f if subject has not started study drug within 7 days after transplant, a quantitative HCV RNA will also be obtained day 7 after transplant

§ proton pump inhibitors, H2 antagonists, and beta blockers **APPENDIX 3a**
Schedule of Assessments for Virologic Failure Substudy

	Day 1 ^a	Wk 1	Wk 4	Wk 8	End of Rx	FU 4	FU 12	FU 24	Early end of Rx or Rx fail
Visit Window (d)	N.A.	4	4	4	4	10	10	10	14
Informed consent	•								
Study drug	•	•	•	•					
Study visit ^b	•	•	• ^c	•	•	• ^c	•		• ^d
Lab visit only ^a								•	
hCG if childbearing potential			•	•	•	•			
HCV RNA	•	•	•		•	•	•	•	•
AE assessment	•	•	•	•	•	•			
Concomitant medications of interest ^e	•	•	•	•	•				

^a Day 1 must occur within 30 days of documentation of virologic failure

^b BUN, creatinine, GFR, INR, sodium, potassium, bicarbonate, ALT, AST, alkaline phosphatase, total bilirubin, albumin, hemoglobin, and immunosuppressant level and dosage.

^c hepatitis B surface antigen added to other evaluations

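### The Virologic Failure Substudy schedules no hCG before the first SOF/VEL/VOX dose; after a relapse first found at follow-up Week 12 or 24, the last scheduled test is about 56-86 or 140-170 days old

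*Combined protocol and SAP*

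**What the plan says.** Under Study Visits for Virologic Failure Substudy, the visit headed "Day 1 (The day SOF/VEL/VOX commences" consists of the first dose, a laboratory panel ending with immunosuppressant level and quantitative HCV RNA, and concomitant medications. It names no hCG. The first one in the substudy text comes under the on-treatment visits: "Serum or urine hCG for females of childbearing potential at weeks 4 and 8". Further tests follow at end of treatment and FU 4.

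Appendix 3a agrees. Its row "hCG if childbearing potential" is blank under Day 1 and Week 1 and is marked at Week 4, Week 8, end of treatment and FU 4. Footnote a sets the timing: "Day 1 must occur within 30 days of documentation of virologic failure".

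In the main study, the last hCG in the visit text is under Post-HCV treatment Follow Up visits: "Serum or urine hCG for females of childbearing potential at Follow Up Week 4". HCV RNA is also tested at FU 12 and FU 24, but no hCG is listed there. The Early End of Treatment or Treatment Failure visit adds genotype and resistance testing but no hCG; "This visit must occur within 2 weeks of stopping treatment or recognition of viral breakthrough or relapse".

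Before the first SOF/VEL dose, the main study tests hCG on the Pre-Transplant Day. Main-study Day 1 lists no hCG of its own but includes "Confirm recipient still meets eligibility criteria". The substudy Day 1 list has no matching line.

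**The concern.** Pregnancy is an exclusion criterion in the main study, and the substudy tests hCG during and after treatment, so pregnancy monitoring is plainly intended. The missing test is the one that could prevent exposure. A subject of childbearing potential whose relapse is first found at FU 12 or FU 24 could begin a second 12-week course with no recent scheduled test, and the next one falls about four weeks into dosing.

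This is a safety matter for a very small group. The documents give no reproductive-toxicity data, so no size of harm can be put on it. The argument rests on consistency with the plan's own monitoring. The SVR12 estimate and its confidence interval are not touched.

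**Working it through.** The plan states no hCG age and no maximum age, so there is no figure of its own to reproduce. The check is calendar arithmetic.

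**Inputs**
- FU visits at 4, 12 and 24 weeks after the last dose: days 28, 84 and 168 (Post-HCV treatment Follow Up visits).
- Last main-study hCG: FU 4, day 28 (same section).
- Documented failure to substudy Day 1: 0 to 30 days (Appendix 3a, footnote a).
- Windows: 10 days either way for FU visits, 4 days for on-treatment visits (Visit Windows).
- Pre-Transplant Day within 24 hours before transplant, and SOF/VEL started up to 4 weeks after it (Study Design).
- Assumption: failure counts as documented on the date of the visit that finds it.

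**Age of the last scheduled hCG at the first SOF/VEL/VOX dose** = (day of the visit finding relapse − 28) + (0 to 30)
- FU 12: 84 − 28 = 56; 56 + 0 to 56 + 30 gives 56-86 days.
- FU 24: 168 − 28 = 140; 140 + 0 to 140 + 30 gives 140-170 days.

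**With visit windows.** Both FU visits can move by 10 days in opposite directions, so by 20 in total.
- FU 12: 56 − 20 = 36 and 86 + 20 = 106, so 36-106 days.
- FU 24: 140 − 20 = 120 and 170 + 20 = 190, so 120-190 days.

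**If failure counts as documented only at the Treatment Failure visit**, up to 14 days later, the nominal upper ends become 86 + 14 = 100 and 170 + 14 = 184 days.

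**Where the gap does not arise.** A failure found at treatment Week 4, end of treatment or FU 4 has an hCG at the same visit, so the test is 0-30 days old at substudy Day 1. The substudy may also use main-study laboratory results when visits coincide. That does not help at FU 12 or FU 24, where there is no hCG to share.

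**Drug taken before the next scheduled hCG.** Week 4 = 4 × 7 = 28 days; with the 4-day window, 24-32 days.

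**Context from the main study.** 1 day + 28 days = 29 days, the oldest the Pre-Transplant Day test can be at the first SOF/VEL dose.

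**How many could be affected.** At the 94% SVR rate the plan cites, 30 × 0.06 = 1.8 subjects fail; at its illustrative 90%, 30 × 0.10 = 3. These counts cover both sexes. The gap needs a failing subject who is also of childbearing potential, is first detected at FU 12 or FU 24, and enters the substudy. The documents give no figures for those steps, so no probability is offered.

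**The case against.** The strongest reply is that pregnancy is already guarded against. Subject Population excludes pregnant subjects and requires two methods of birth control. Subject Enrollment makes the investigator responsible for eligibility throughout the study. Retreatment is at the principal investigator's discretion and follows a separate consent with a review of risks. A clinical examination is due at the Treatment Failure visit. All of this stands, and an investigator may order an unscheduled test. None of it schedules one.

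The visit lists are also imperfect evidence. The substudy Day 1 list omits informed consent and adverse event assessment, yet Appendix 3a marks both on Day 1. For hCG, however, list and grid agree. The copy reviewed lacks the main-study grid (Appendix 3) and the substudy consent form. An hCG mark in that grid at FU 12, FU 24 or the failure visit would shorten the ages above, though it would not fill the blank Day 1 cell in Appendix 3a.

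Two stronger readings are tempting:
- A reader might infer that the substudy breaks a 29-day limit. The protocol sets no such limit: the figure follows from two other timing rules, and main-study Day 1 has no hCG either. It is context only.
- A reader might infer that the plan contradicts itself, because Clinical Evaluations lists "serum or urine serum hCG for females of childbearing potential at weeks 4 and 8 and at end of treatment" and does not mention FU 4. That list is introduced as data reviewed from the medical record, and its post-transplant part also omits the hepatitis B surface antigen tests that the visit text schedules at Week 4 and FU 4. It is better read as an incomplete summary than as a rival schedule, and the visit text governs.

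**Conclusion.** The omission is real and narrow. Followed as written, the schedule puts no hCG between FU 4 of the main study and Week 4 of SOF/VEL/VOX for a relapse first found at FU 12 or FU 24. The sizes are those worked out above; even the smallest, 36 days, exceeds the 29 days seen in the main study. They rest on the visit text, on dating documentation to the visit, and on there being no extra hCG in the pages not available.

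A reader might infer that every retreated subject is affected, or that the plan permits dosing with no pregnancy check at all. Neither follows. Failures found at Week 4, end of treatment or FU 4 have a same-visit test, and the general safeguards remain in force. What is missing is a scheduled hCG before the first dose. With few subjects affected, perhaps none, and no effect on SVR12, this is a low-priority improvement worth making because it is so easy.

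**What to change.** In the substudy Day 1 list, add a serum or urine hCG for subjects of childbearing potential, with the result known before the first tablet is taken. Mark Day 1 in the hCG row of Appendix 3a to match. With the sample taken on Day 1, the age of the test at first dose falls to 0 days whichever visit found the relapse.

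The cost is one additional hCG per substudy subject of childbearing potential, at a visit where blood is already drawn, plus one line of text and one table mark. No visit is added. The first dose must wait for the result, so Day 1 should be planned to leave room for it within the 30-day limit.
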